11.5.4 Dose Delays and Modifications for DS-3201b

During Cycle 1 of Phase I dose-escalation, which includes the initial 7 days of safety run-in from Day -7 to Day 0, dose delays and modifications for DS-3201b will not be used unless a DLT has been declared for purposes of determining the MTD. The outlined dose delays and modifications for both DS-3201b and irinotecan will be used in all patients in Phase I Cycle 1 if DLT has been declared, in all subsequent cycles of Phase I, and in all cycles of Phase II of this study. If toxicities are encountered, dosing adjustments and delays of DS-3201b and/or irinotecan will be made based on determination of the likely causative agent as outlined above in Sections 11.2 and 11.3. Determination of the likely causative agent will be dependent on the treating physician if they feel that the toxicity is at least possibly related to either or both of the study drugs.

Please refer to Table 2 in Section 9.0 for full details regarding the dose levels for DS-3201b. An abbreviated version of Table 2.0 is shown below for reference.

Dose Level	DS-3201b Dose
Level -1	50 mg once daily
Level 1(Starting Dose)	100 mg once daily
Level 2	150 mg once daily
Level 3	200 mg once daily
Level 4	250 mg once daily
Level 5	300 mg once daily

If dose level reduction below Level -1 is needed to manage toxicity due to DS-3201b, then study treatment with both DS-3201b and irinotecan will be permanently discontinued unless discussed with the study PI.

Table 5.0 Dose Delays and Modifications for Hematologic TEAEs

ADVERSE EVENT GRADE	DOSE MODIFICATION INSTRUCTIONS
≥Grade 4 neutropenia (<0.5 x 10 ⁹ /L per NCI CTCAE v5.0) lasting >7 days	
• Interrupt administration of study drug DS-3201b up to 28 days.• Resume the study drug DS-3201b at the dose before interruption if lasting ≤7 days at a reduced dose (by 1 dose level). If lasting >7 days once resolved to ≤Grade 2
OR	

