Although all toxicities will be closely monitored and graded throughout the entire study treatment, only toxicities occurring during Cycle 1 of treatment (initial 7-day safety run-in plus the first 21 days) that meet the definition of DLT will influence the determination of MTD. Any toxicity during Cycle 1 of treatment that meets the definition of DLT as described below, whether it is attributed to either DS-3201b or irinotecan or both, will affect the determination of MTD during the Phase I portion of the study.

Dose-limiting toxicity (DLT) is defined as a clinically significant non-hematologic treatment-emergent adverse event (TEAE) or abnormal clinical laboratory value that is clearly **NOT** related to disease progression, intercurrent illness, and occurring during the DLT evaluation period (safety run-in + Cycle 1) on study that meets any of the following criteria:

Hematologic dose-limiting toxicity is defined as any:

- All Grade ≥ 3 adverse event that are at least possibly related to study treatment with the following exceptions:
 - Grade 4 neutropenia lasting less than 7 consecutive days.
 - Grade 3 neutropenia without fever and/or infection where fever is an oral temperature $\geq 38.5^{\circ}\text{C}$.

- Grade 4 thrombocytopenia (platelet count<25,000/mm³) lasting less than 7 consecutive days. *However, a platelet count <10,000/mm³ at any time for any duration will count as a DLT.*
- Grade 3 thrombocytopenia without bleeding.

Non-Hematologic dose-limiting toxicity is defined as any:

- All Grade ≥3 adverse events that are at least possibly related to study treatment with the following exceptions:
 - Grade 3 aspartate aminotransferase AST (SGOT) or alanine aminotransferase (ALT) (SGPT) or bilirubin for ≤ 7 days.
 - Grade 3 or 4 nausea, vomiting, and diarrhea that do not require hospitalization or total parenteral nutrition (TPN) support and can be managed with supportive care to ≤ Grade 2 within 48 hours.
 - Electrolyte abnormalities that are corrected to ≤ Grade 2 within 24 hours.
 - Alopecia and study drug-related fever (without Grade 3 neutropenia) will not constitute DLT.
 - Any Grade 5 adverse event proven to be clearly and incontrovertibly related to disease progression or intercurrent illness and not possibly related to study drug DS-3201b.

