If the treating physician determines that a TEAE occurring during the DLT evaluation period which met the definition for DLT is due to underlying disease progression or intercurrent illness and NOT due to study drug effect from either DS-3201b and irinotecan, a final determination regarding DLT determination will be discussed with the study PI.

Patients who are unable to complete at least 75% of the prescribed dose (i.e., 21 days) of DS-3201b and irinotecan during the DLT evaluation period (safety run-in + Cycle 1) due to non-disease-related ≥ Grade 2 adverse events will be considered to have a DLT. These same DLT definitions detailed above in this section will also apply for the entire duration of the Phase II portion of the study as it pertains to the toxicity stopping rule (please see Section 14.0 for more details).

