13.1 CRITERIA FOR REMOVAL FROM STUDY

Study treatments will be discontinued for all patients in the following situations:

- Disease progression
- General or specific changes in the patient's condition render the patient unacceptable for further treatment in the judgment of the investigator
- Unacceptable adverse event(s)
- Inability of patient to comply with study requirements

In addition to the above, patients may withdraw from the study at any time for any reason. Once decision has been made to stop study drug treatment, the treating physician will report on the date of last treatment and the reason for cessation of study drug treatments. Patients who are no longer receiving study drugs will still be followed clinically for toxicity and survival endpoints, unless the patient explicitly declines.

Procedures for Study Withdrawal

Withdrawal procedures will include an end-of-treatment (EOT) visit within 30 days of the last dose of study drug.

Replacement of Patients

During both Phase I and II of the study (dose-escalation), any patient who discontinues treatment before completing the first cycle of treatment (C1D21) will be considered not evaluable for DLT and will be replaced. Completion of the first cycle of treatment is defined by completion of at least 75% of both study drugs during the initial 28-Day DLT evaluation window (7-day safety run-in + 21-day Cycle 1). The only exception are patients who are unable to complete at least 75% of the prescribed dose of DS-3201b and irinotecan during the DLT evaluation period (safety run-in + Cycle 1) due to non-disease-related \geq Grade 2 adverse events; these patients will be considered to have a DLT and will not be replaced. Please see Section 11.0 for the full definition of DLTs.

During Phase II of the study, any patient who discontinues treatment before completing two cycles of treatment but has completed the DLT evaluation period will still undergo the first repeat CT scan prior to their scheduled C3D1. If a CT scan evaluation is unable to be obtained, these patients will not be replaced, and they will be considered as not deriving clinical benefit from the study drug.

Re-screening of Patients

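### The DLT definition exempts a brief Grade 4 platelet or neutrophil count with low-grade bleeding or infection, while the same complication at a Grade 3 count is a DLT

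*Combined protocol and SAP*

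**What the plan says.** Under Definitions of Dose-Limiting Toxicity (printed as 11.9 8), every haematologic event of Grade 3 or higher that is at least possibly related to treatment is a DLT, with four exceptions:

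- "Grade 4 neutropenia lasting less than 7 consecutive days"
- "Grade 3 neutropenia without fever and/or infection where fever is an oral temperature" of at least 38.5 °C
- "Grade 4 thrombocytopenia (platelet count<25,000/mm³) lasting less than 7 consecutive days", except that any platelet count below 10,000/mm³ is a DLT whatever its duration
- "Grade 3 thrombocytopenia without bleeding"

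Non-haematologic events become DLTs only from Grade 3. A separate rule makes a DLT of any patient "unable to complete at least 75% of the prescribed dose (i.e., 21 days) of DS-3201b and irinotecan during the DLT evaluation period" because of non-disease-related adverse events of Grade 2 or higher. Section 13.1 defines finishing the first cycle as "completion of at least 75% of both study drugs during the initial 28-Day DLT evaluation window".

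The same section carries the list into Phase II: "These same DLT definitions detailed above in this section will also apply for the entire duration of the Phase II portion of the study", for the purpose of the toxicity stopping rule. Section 14.0 sets that rule at 2 DLTs in 5 newly recruited patients, 3 in 10, 3 in 15, 3 in 20 and 4 in 25. Section 9.1 reports dose escalation complete, with 100 mg daily selected.

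**The concern.** A toxicity definition should not become more lenient as the count worsens. Here the two Grade 3 exemptions are lost once a complication appears, but the two Grade 4 exemptions are not. A patient with the deeper count and the same low-grade bleed or infection can therefore be left out of a count that includes the milder case.

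The count feeds a rule with boundaries of 2 to 4 events in at most 25 patients, so one patient's classification can decide whether a boundary is crossed. With two sites in Phase II, the same event could also be classified differently depending on how literally the list is read.

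**Working it through.** **1. Apply the exemptions.** Take a 3-day event with platelets of at least 10,000/mm³. Grade limits are those of Tables 5.0 and 8.0: platelets below 50,000 (Grade 3) and below 25,000 (Grade 4); neutrophils 500-999 (Grade 3) and below 500 (Grade 4).

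| Count | Complication | DLT under the list? |
|---|---|---|
| Platelets 40,000 (Grade 3) | none | no |
| Platelets 40,000 (Grade 3) | Grade 1-2 bleed | **yes** |
| Platelets 20,000 (Grade 4) | none | no |
| Platelets 20,000 (Grade 4) | Grade 1-2 bleed | **no** |
| Neutrophils 700 (Grade 3) | Grade 2 infection | **yes** |
| Neutrophils 300 (Grade 4) | Grade 2 infection, no febrile neutropenia | **no** |

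**2. Limit the gap.** These already count: platelets below 10,000/mm³; Grade 4 counts of 7 days or more; bleeding or infection of Grade 3 or higher that is at least possibly related to treatment; and febrile neutropenia of Grade 3 or higher as an event in its own right.

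**3. Test the 75%-dose rule as a backstop.** The window is 7 + 21 = 28 days of DS-3201b and 2 irinotecan doses.

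- Day 8 irinotecan omitted: 1/2 = 50%, a DLT.
- DS-3201b held Cycle 1 Days 14-21: 8 days lost, 20/28 = 71.4%, a DLT.
- DS-3201b held Cycle 1 Days 15-21: 7 days lost, 21/28 = 75.0%, which meets the threshold. Both irinotecan doses have been given, so this is not a DLT.

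The last line assumes that no earlier dose was missed. One earlier DS-3201b dose lost to a qualifying adverse event gives 20/28 = 71.4%, a DLT. The rule is also worded for the run-in plus Cycle 1, so its reach into later Phase II cycles is unclear.

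**4. Reproduce the plan's stopping table.** Let f(i, k) be the probability of k DLTs after i patients without having stopped. Then f(i, k) = (1 − p)·f(i − 1, k) + p·f(i − 1, k − 1). At i = 5, 10, 15, 20, 25, move the mass at k ≥ 2, 3, 3, 3, 4 to stopped. At p = 0.05 the first look gives 1 − 0.95⁵ − 5(0.05)(0.95⁴) = 0.0226. The five looks sum to 0.0226 + 0.0055 + 0.0209 + 0.0364 + 0.0045 = 0.0899.

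| True DLT rate | 0.05 | 0.09 | 0.13 | 0.17 | 0.21 | 0.25 |
|---|---|---|---|---|---|---|
| Plan | 0.09 | 0.30 | 0.54 | 0.74 | 0.87 | 0.94 |
| Recomputed | 0.090 | 0.301 | 0.541 | 0.736 | 0.865 | 0.938 |

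The table reproduces to within about 0.005.

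**5. Illustrate the size.** No rate for these events is given. Assume, for illustration only, that 1 to 2 percentage points of patients have one and nothing else that counts.

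| Rate if the events count | Rate as written | P(stop) if the events count | P(stop) as written |
|---|---|---|---|
| 21% | 20% to 19% | 0.865 | 0.839 to 0.809 |
| 17% | 16% to 15% | 0.736 | 0.694 to 0.647 |

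The same assumption prices the fix when the rate as written is low.

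| Rate as written | Rate after the fix | P(stop) as written | P(stop) after the fix |
|---|---|---|---|
| 9% | 10% to 11% | 0.301 | 0.36 to 0.42 |
| 5% | 6% to 7% | 0.090 | 0.13 to 0.19 |

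**The case against.** **The gap is narrow, and patients are managed anyway.** This stands. Grade 4 thrombocytopenia interrupts DS-3201b under Table 5.0, and Section 11.5.4 holds irinotecan with it. Table 5.0 is entered for neutropenia at "≥Grade 4 neutropenia (<0.5 x 10 ⁹ /L per NCI CTCAE v5.0) lasting >7 days", for febrile neutropenia or for G-CSF use, so brief Grade 4 neutropenia falls mainly to irinotecan Table 8.0. Table 6.0 adds an interruption for any event of substantial clinical risk, and the institutional DSMC oversees the trial (Section 16.3). A reader might infer that affected patients go on being dosed unprotected; the documents do not support that. But none of these provisions sets the DLT count.

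**A Grade 4 episode passes through Grade 3 and could be counted there.** The text does not exclude this reading. It does not state it either, and it gives Grade 4 its own exemptions.

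**The 75%-dose rule sits directly above the sentence extending the definitions to Phase II, and may apply there too.** That is arguable. Even so, it captures only events that cost enough dosing.

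**The fix costs about as much as it gains.** On the same assumed points, stopping rises by 0.03-0.06 at 21% and 0.04-0.09 at 17%, but also by 0.06-0.12 at 9% and 0.04-0.10 at 5%. Two Grade 1 bleeds during brief Grade 4 counts in the first five patients would stop the trial. This is fair, so the case for change rests on a coherent event count and not on better stopping probabilities. Two Grade 1 bleeds at Grade 3 counts already stop the trial today.

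**Conclusion.** The inconsistency is certain on a literal reading: the definition is wrong as written. Severity is low. The affected events are narrow, their frequency is unknown and the effect is probably small. The probability shifts rest wholly on the assumed 1 to 2 points.

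Two stronger conclusions are tempting and unsupported. The first is that the stopping table is wrong. It is not: it reproduces and is correct for any given DLT rate, and the only question is which events are counted. The second is that the selected Phase II dose is unsound. The same definition governed Phase I, but escalation is complete and the documents report no event of this kind in it.

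**What to change.** Add *and without bleeding* to the Grade 4 thrombocytopenia exemption, and *and without fever and/or infection* to the Grade 4 neutropenia exemption. Keep the duration limits, the 10,000/mm³ floor, the stopping boundaries and the operating-characteristics table as they are. The fever part is mainly harmonisation, since febrile neutropenia of Grade 3 or higher already counts.

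Do not import Table 5.0's Grade 2 bleeding threshold into the platelet exemptions. Applied at both grades, it would newly exempt Grade 3 thrombocytopenia with a Grade 1 bleed, which is a DLT today.

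The cost is a two-phrase amendment and somewhat more stopping at acceptable DLT rates, as illustrated in the working. For Phase II patients already treated, bleeding and infection records must be re-read alongside the Grade 4 counts. The recount could cross a boundary after the fact, so the amendment should say how that would be handled.

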
6.1 CRITERIA FOR SUBJECT ELIGIBILITY

6.2 Subject Inclusion Criteria

- Signed informed consent form (ICF)
- Ability to comply with the study protocol as per the investigator's judgment
- Age \geq 18 years at the time of signing the ICF
- Life expectancy \geq 12 weeks
- Karnofsky performance status \geq 70% or ECOG 0, 1 or 2.
- Pathologically confirmed diagnosis of small cell lung cancer. Patients with a diagnosis of combined small cell lung cancer with other histologies may be considered for

inclusion if the predominant histology is SCLC and only after discussion with the study PI. Patients with transformed SCLC from NSCLC are allowed on study after discussing with the MSKCC or JHU Study PI.

- Radiographically documented progression of disease after prior treatment with a platinum doublet regimen. Patients who received a platinum doublet regimen in combination with immunotherapy are still eligible for the study.
- Measurable disease according to RECIST v1.1
- Adequate tissue sample available for both IHC testing of IHC testing of SLFN11 and H3K27me3 and molecular profiling (archived tissue block or 20 unstained slides). Tissue sample can be either from an initial pre-platinum-based chemotherapy sample OR from a repeat biopsy sample after progression on platinum-based chemotherapy.
- Concurrent consent to the appropriate biospecimen research protocols at MSKCC (#06-107 Storage and Research Use of Human Biospecimens) and at JHU.
- Adequate hematologic and end-organ function, as defined by the following laboratory test results obtained within 14 days prior to initiation of study treatment:
 - Adequate bone marrow function as defined by:
 - Absolute neutrophil count (ANC) $\geq 1.5 \times 10^9/L$ ($1500/\mu L$) without granulocyte colony-stimulating factor support within 2 weeks prior to starting study therapy
 - Hemoglobin $\geq 9 \text{ g/dL}$ (transfusions to meet this criterion are allowed)
 - Platelets $\geq 150 \times 10^9/L$ without transfusion
 - Adequate renal function as defined by:
 - Creatinine clearance $\geq 30 \text{ mL/min}$ as calculated using the modified Cockcroft-Gault equation or Modification of Diet in Renal Disease (MDRD) formula OR serum creatinine $\leq 1.5 \times \text{ULN}$
 - Adequate hepatic function as defined by:
 - AST, ALT, and alkaline phosphatase (ALP) $\leq 3 \times \text{ULN}$ with the following exceptions:
 - Patients with documented liver metastases: AST, ALT and ALP $\leq 5 \times \text{ULN}$

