11.3.2 Possible Treatment Emergent Adverse Events (TEAEs) for DS-3201b

COMMON:

- Platelet Count Decreased
- Altered taste (Dysgeusia)
- Anemia
- Neutrophil Count Decreased
- Alopecia
- White Blood Cell Count Decreased
- Lymphocyte Count Decreased
- Diarrhea
- Nausea

OCCASIONAL (Uncommon):

- Alanine Aminotransferase Increased
- Aspartate Aminotransferase Increased
- Decreased Appetite
- Common cold (Nasopharyngitis)
- Cough
- Fatigue
- Arthralgia
- Dyspnea
- Fever (Pyrexia)
- Pruritus
- Rash
- Dry Skin
- Gamma-Glutamyltransferase Increased

RARE:

- None

Contraindications regarding the use of DS-3201b in human subjects have not been established. DS-3201b is contraindicated for subjects with known hypersensitivity to either the drug substance or inactive ingredients in the drug product. No overdosages have been reported to date.

ADVERSE EVENTS OF SPECIAL INTEREST (AESI):

AESI include hepatic events that meet the potential Hy's Law criteria (defined as an elevated ALT and/or AST $\geq 3 \times$ ULN and an elevated TBL $> 2 \times$ ULN, regardless if it is due to disease progression per investigator assessment, which may occur at different time points during the study conduct), and secondary malignancy, including lymphoid malignancy.

Combined Elevations of Aminotransferases and Bilirubin

Hepatic events (both serious and non-serious) that meet the potential Hy's Law criteria defined as an elevated (ALT and/or AST) $\geq 3 \times$ ULN and an elevated TBL $> 2 \times$ ULN, regardless if it is due to disease progression per investigator assessment, that may occur at different time points during the study conduct, should always be reported to the sponsor. These events must be reported by eCRF, with the investigator's assessment of seriousness, severity, causality, and a detailed narrative. These events should be reported within 24 hours of investigator's awareness of the event regardless of seriousness.

If the subject discontinues study drug due to liver enzyme abnormalities, the subject should have additional clinical and laboratory evaluations in order to determine the nature and severity of the potential liver injury (including follow-up ALT, AST, TBL (including fractional), ALP and relevant hepatitis serology).

Secondary Malignancy

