If DS-3201b needs to be held for any TEAEs as above, irinotecan should be held as well. When both study drugs are held for any particular visit due to TEAEs, counting of dose cycles will hold until their TEAEs have resolved or improved enough to meet protocol guidelines to restart treatment with both study drugs. If both drugs are held longer than 1 cycle (21 days), the treating physician must discuss eligibility for the patient to continue treatment on study with the study PI.

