Study enrollment of the 17th patient will be suspended until the determination of the first-stage results, unless the benchmark of 3 patients with radiographic response is achieved by then. All patients will be included in the primary analysis, even if there are major protocol deviations. Patients are considered non-responses (PD) if they are not evaluable (including if CT scan evaluation not available) or died during the study. This study requires accrual of a minimum of 16 patients and up to a maximum of 31 patients if the cohort is expanded to the second stage. The accrual time is estimated to be between 10-24 months at the rate of 3 patients per month and a likely planned 4 months suspension between the first and second stages of this Phase II study.

To protect patients from excessive toxicity, a stopping rule for toxicity will be implemented during Phase II. Since the 6 patients treated at RP2D in Phase I will be included in the Phase II portion of the study, the early stopping rule for toxicity is calculated based on 31-

6=25 newly recruited patients. This toxicity rule will apply for the entire duration of the Phase II portion of the study.

Stopping rule:

Number of recruited patients	5	10	15	20	25
Number of DLT to stop the trial	≥2	≥3	≥3	≥3	≥4

Operating characteristics of the stopping rule:

True DLT rate	0.05	0.09	0.13	0.17	0.21	0.25
Probability of stopping the trial	0.09	0.30	0.54	0.74	0.87	0.94

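### The DLT exemption for Grade 3 AST, ALT or bilirubin lasting up to 7 days is not limited to isolated rises, so a short related event meeting potential Hy's Law criteria can go uncounted in the Phase II stopping rule (minor)

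*Combined protocol and SAP*

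**What the plan says.** The DLT definitions (printed as Section 11.9 8) start from a broad non-hematologic rule, "All Grade ≥3 adverse events that are at least possibly related to study treatment with the following exceptions". One of the exceptions is "Grade 3 aspartate aminotransferase AST (SGOT) or alanine aminotransferase (ALT) (SGPT) or bilirubin for" at most 7 days. It does not require the rise to be isolated and does not mention Hy's Law.

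Section 11.3.2 defines the potential Hy's Law pattern as an adverse event of special interest: ALT and/or AST at least 3x ULN together with total bilirubin above 2x ULN, whether or not due to progression and possibly at different time points. Its consequence is expedited reporting: "These events should be reported within 24 hours of investigator's awareness of the event regardless of seriousness". Nothing there or elsewhere makes the pattern a DLT.

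The DLT definitions "will also apply for the entire duration of the Phase II portion of the study as it pertains to the toxicity stopping rule". Section 14.0 says of the rule itself: "This toxicity rule will apply for the entire duration of the Phase II portion of the study". The rule covers 25 newly recruited patients and stops at 2 DLTs in 5 patients, 3 in 10, 15 or 20, and 4 in 25.

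**The concern.** Raised transaminases with raised bilirubin are the one liver pattern that the protocol marks for urgent attention, yet a short Grade 3 episode of it falls inside an exemption from the DLT count. Phase II stops on 2 to 4 DLTs, so one event more or less can decide whether a boundary is met. At stake is only whether such an event adds to that count.

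**Working it through.** **Does any other text bring the event back into the count?**

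- *Severity and duration.* The exemption covers Grade 3 for up to 7 days. Grade 4 rises and longer Grade 3 rises remain DLTs.
- *75% dose rule (DLT definitions; Section 13.1 applies it to both drugs).* The window is 7 + 21 = 28 days. Missing 7 days of DS-3201b leaves 21/28 = 75%, which passes. Missing 8 leaves 20/28 = 71%, which is a DLT. Cycle 1 has two irinotecan doses, so one omitted and not made up leaves 1/2 = 50%, also a DLT. The rule therefore catches some Cycle 1 events. It misses those that cost little dosing, and how it works after Cycle 1 is unclear.
- *Discussion with the study PI (DLT definitions).* This concerns events that already met the definition and may be due to progression or intercurrent illness. It cannot add an exempted event.
- *Separate term.* A related Grade 3 or higher event recorded under another name, such as liver injury, is not in the exception list and would count.

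A related, short Grade 3 event meeting the Section 11.3.2 criteria and caught by none of these stays out.

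**Reproducing the plan's table.** Inputs from Section 14.0: looks at 5, 10, 15, 20 and 25 patients, boundaries 2, 3, 3, 3 and 4. Exact recursion: add five patients as Binomial(5, p), sum the probability at or above the boundary, remove those paths, and continue. At p = 0.05 the five looks contribute 0.0226 + 0.0055 + 0.0209 + 0.0364 + 0.0045 = 0.0899.

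| True DLT rate | 0.05 | 0.09 | 0.13 | 0.17 | 0.21 | 0.25 |
|---|---|---|---|---|---|---|
| Stated | 0.09 | 0.30 | 0.54 | 0.74 | 0.87 | 0.94 |
| Recomputed | 0.090 | 0.301 | 0.541 | 0.736 | 0.865 | 0.938 |

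The table is correct for whatever is counted. The point concerns what is counted.

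**Illustration of size.** Let p be the rate of DLTs that count as written and h the rate of exempted potential Hy's Law events. The values of h are assumptions, and independence is assumed. If the events counted, the rate would be q = 1 − (1 − p)(1 − h). For example, p = 0.09 and h = 0.01 give q = 1 − 0.91 × 0.99 = 0.0991.

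| Other DLTs (p) | As written | h = 0.5% | h = 1% | h = 2% |
|---|---|---|---|---|
| 0.05 | 0.090 | 0.110 | 0.132 | 0.180 |
| 0.09 | 0.301 | 0.329 | 0.357 | 0.413 |
| 0.13 | 0.541 | 0.565 | 0.589 | 0.634 |
| 0.17 | 0.736 | 0.753 | 0.768 | 0.797 |

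The chance of at least one such event in 25 patients is 1 − (1 − h)^25 = 0.118, 0.222 or 0.397. At these rates, the chance that the trial sees none is 60% to 88%.

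**The case against.** The strongest reply is that a wide net for reporting and a narrower one for stopping is a coherent choice. The Section 11.3.2 definition is deliberately broad, taking in progression and rises at different times, whereas a DLT must be related and not due to progression. That stands as a reason not to import the reporting definition whole. It does not explain why a related Grade 3 event with both rises should be exempt.

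Dose holds also protect more than the exemption suggests. Table 6.0 holds DS-3201b for a drug-related Grade 3 laboratory event that requires treatment until Grade 1 or baseline, so a hold can outlast the Grade 3 period and trigger the 75% rule; "If DS-3201b needs to be held for any TEAEs as above, irinotecan should be held as well". This stands for part of Cycle 1. It does not reach rises needing no treatment, events late in the cycle, or irinotecan doses delayed and then given. Panels from Cycle 2 are scheduled only on Days 1 and 8 (Table 3.0), so a rise first seen on Day 8 may not be shown to be short without extra tests. That narrows the gap further without closing it.

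Four stronger readings are tempting but not supported:

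- *The platelet line shows an inconsistency.* A reader might note that counts below 10,000/mm³ "at any time for any duration will count as a DLT". That override qualifies an exemption for Grade 4 thrombocytopenia. The liver exemption never reaches Grade 4, so the missing parallel is not an inconsistency.
- *The two sites will classify events differently.* Nothing in the documents shows this. There is one database and DSMC review, and each potential Hy's Law event is reported with a causality assessment and narrative.
- *Patients are unprotected.* The 24-hour reporting and the dose-hold tables apply regardless of DLT status.
- *The Phase I dose is in doubt.* The same wording applied there, but escalation is complete and the documents describe no such event.

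**Conclusion.** The gap is real and minor. It rests on the wording alone: the exemption has no limit to isolated rises, no Hy's Law exclusion exists in the DLT definitions, and the same definitions feed the Phase II rule. Alpha, power, sample size, the boundaries and the stated operating characteristics are unaffected. The changes in stopping probability are illustrative only, because no rate for these events is given. Section 11.3.2 lists ALT and AST increases for DS-3201b as occasional and does not list bilirubin, so most often the rule would act the same either way.

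**What to change.** Reword the one exception, for example:

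*Grade 3 AST, ALT or bilirubin for up to 7 days, unless ALT and/or AST at least 3x ULN and total bilirubin above 2x ULN occur in the same episode; for a patient whose baseline value is above ULN, that value must also have risen by a stated multiple of baseline (for example at least 1.5x).*

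Keep the existing Grade 3 or higher, relatedness and not-due-to-progression conditions, and do not add a free-standing criterion without a grade floor. The same-episode condition is needed because Section 11.3.2 allows the two rises at different times. The baseline condition is needed because Section 6.2 admits raised values: "Patients with documented liver metastases: AST, ALT and ALP" up to 5x ULN, and any patient with total bilirubin up to 2.0 mg/dL. Assuming a bilirubin ULN of 1.0 to 1.2 mg/dL, 2x ULN is 2.0 to 2.4 mg/dL. From a baseline of 2.0, a rise of about 0 to 0.4 mg/dL would otherwise be enough. The 1.5x multiple is an example for the clinical team to settle.

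The cost is one sentence and no new data collection, since AST, ALT and bilirubin are already in the panel at each scheduled visit. The downside is slightly more frequent stopping of a tolerable regimen: at a 5% rate of other DLTs, 0.09 becomes 0.11, 0.13 or 0.18 at the assumed event rates of 0.5%, 1% or 2%.
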